### 2.2.4.1. Summary of Clinical Safety

Study C4611007 consisted of 2 interleaving cohorts with a total of 15 healthy adult participants evaluable for safety data. Single doses of PF-07304814 ranging from 50 to 700 mg were evaluated. At the 50 mg and 500 mg dose level 6 participants were exposed to study drug, at the 150 mg and 700 mg dose level 5 participants were exposed to study drug; 2 participants were exposed to placebo at each dose level.

Following a single 50, 150, 500, or 700 mg dose of PF-07304814 administered as a 24-hour infusion in healthy participants, a total of 20 all-causality treatment emergent adverse events (TEAEs) were reported by 12 participants across the different treatment groups. There were no deaths, serious adverse events (SAEs), severe AEs or discontinuations due to AEs during this study. There were no individual laboratory abnormalities assessed as clinically significant by the Investigator.

In the ongoing study in hospitalized COVID-19 patients (C4611001), as of the data cut-off snapshot (26 March 2021), 8 participants have been enrolled in Part 1 and 8 participants in Part 2. In Part 1, 4 participants were dosed at 250 mg dose (PF-07304814 or placebo) and 4 participants were dosed at 500 mg dose (PF-07304814 or placebo) in a blinded manner. In Part 2, 6 participants were dosed with PF-07304814 at 250 mg/day for 5 days (~120-hour infusion) and 2 participants received placebo for the same duration, in a blinded manner.

Seven TEAEs were reported by 3 participants in Part 1 (24 hour infusion), 250 mg does cohort. Four AEs were considered mild; 1 AE of coagulopathy was considered moderate, and 2 AEs respiratory failure and worsening of COVID pneumonia, were severe. AE of worsening of COVID pneumonia was considered serious (SAE). Except for 1 AE of hematuria experienced by 1 participant, all other AEs were not related to study treatment. In Part 1 (24-hour infusion), 500 mg dose cohort, 12 TEAEs were reported by 3 participants. Ten AEs were mild and 2 were severe and serious (SAEs). None of the AEs were considered treatment-related. Two SAEs of deep venous thrombosis (DVT) of the subclavian vein at the site of the midline placement occurred in 2 participants, 1 of whom was dosed with 500 mg PF-07304814 and the other participant received placebo (sentinel group within the cohort).

In Part 2 (120-hour infusion) 250 mg/day cohort of the ongoing study C4611001, complete data were available from first 6 participants enrolled in the cohort. Of these 6 participants, a total of 2 TEAEs were reported by 1 participant. Both of the AEs were considered to be unrelated to study treatment. Additional, preliminary SAE data were available after the snapshot date (26 March 2021) from last 2 participants enrolled in the cohort. Overall, 3 SAEs were reported by these 2 participants. One participant reported acute respiratory distress syndrome and experienced ventilator-associated pneumonia and the other participant experienced worsening of dyspnea. None of these SAEs were considered related to study treatment.

The preliminary and cumulative data from studies C4611007 and C4611001 show a safety profile that supports continued investigation of PF-07304814 in clinical studies. More detailed information about the known and expected benefits and risks and reasonably expected AEs of PF-07304814 can be found in the IB.

#### **2.2.4.2. Summary of Clinical Pharmacology**

Following single ascending 24-hour IV infusions of PF-07304814 to healthy participants at doses of 50 mg, 150 mg, 500 mg, and 700 mg, near maximum plasma concentrations for PF-00835231 (the active moiety) were generally first observed ~6h post start of the infusion and sustained until the end of the infusion. PF-00835231 plasma concentrations declined rapidly after the end of the infusion with mean  $t_{1/2}$  values of 1.97 hours and 1.74 hours for the 500 mg and 700 mg doses, respectively where these could be calculated and reported. PF-00835231 systemic exposure based on geometric mean  $AUC_{last}$  and  $C_{max}$  values appeared to increase in a dose proportional manner across all doses. Geometric mean  $C_{ss}$  values also increased in a dose proportional manner across all doses. Based on the geometric mean Ae%, approximately 9%-11% of the PF-07304814 dose was recovered in urine as the active moiety PF-00835231 across all doses.

Following single ascending 24-hour IV infusions of PF-07304814 (a phosphate prodrug) at doses of 50 mg, 150 mg, 500 mg, and 700 mg, geometric mean  $C_{max}$  were observed between a median  $T_{max}$  of 3 to 16 hours post start of the infusion. Near maximum plasma concentrations of the phosphate prodrug PF-07304814 were generally first observed ~3 hours and sustained until at least 16 hours post start of the infusion. Despite a continuous 24-hour infusion of PF-07304814, plasma concentrations declined before the end of the infusion.  $t_{1/2}$  values could not be determined since all plasma samples collected after the 16 hours post start of the infusion were below the limit of detection. PF-07304814 systemic exposure based on geometric mean  $AUC_{last}$  values appeared to increase in a dose proportional manner between the 150 mg and 700 mg doses, however this relationship could not be fully assessed for the 50 mg dose due to the high variability and levels being close to or near the lower limit of detection (40 ng/mL). Geometric mean  $C_{max}$  values and  $C_{ss}$  appeared to increase in a dose proportional manner across the dose range studied.

Further details may be found in the IB.

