- h. Urine drug and cotinine (mandatory) and alcohol urine test (at discretion of investigator) will be performed at Screening and on Day -1. These tests may be performed at any other time at the discretion of the investigator.
- i. All ECG assessments will be made after at least a 5-minute rest in a supine position and prior to any blood draws or vital sign measurements.
- j. Single supine blood pressure and pulse rate will be performed following at least a 5-minute rest in a supine position. BP and PR assessments will be performed after collection of ECGs and prior to collection of blood draws if scheduled at the same time.
- k. Check exposure to positive case, residence or travel in area of high incidence and COVID-19 related signs and symptoms. To be done at screening and at Day -1.
- l. The testing for COVID-19 pathogen by RT-PCR will be performed prior to being admitted to the clinic for confinement and a subsequent COVID-19 test will be performed after approximately 4 days (ie, upon completion of 4 × 24 hours in house), or if they develop COVID-19 like symptoms.
- m. To be done at least daily during residence. On days in which vitals are being collected, temperature will only need to be taken once and documented.
- n. PF-07304814 will be administered as a constant-rate, continuous IV infusion, over 24 hours.
- o. One (approximately 4 mL) blood sample for unlabeled PF-07304814 and PF-00835231PK and one (approximately 4 mL) blood sample for PK of total [C] analysis will be taken at the following timepoints: pre-dose (a single approximately 20 mL sample will be collected), and at 0.5, 1, 2, 6, 12, 24 (to be taken immediately prior to end of infusion), 25, 27, 32, 48, 72, 96, 120, 144, and 216 hours post the start of infusion. One (approximately 4 mL) blood sample will be collected at screening to measure the total radioactivity.
- p. One (approximately 10 mL) blood sample will be collected at the times specified in the table for metabolite profiling.

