**Table 1. Pharmacokinetic Parameters**

Parameter	Definition	Method of Determination
$C_{\max}$	Maximum observed plasma concentration	Observed directly from data
$T_{\max}$	Time for $C_{\max}$	Observed directly from data as time of first occurrence
$C_{24}$	Obsereved plasma concentration at 24 hours	Observed directly from data
$t_{1/2}^a$	Terminal elimination half-life	$\log_2(2)/k_{el}$ , where $k_{el}$ is the terminal phase rate constant calculated by a linear regression of the log-linear concentration-time curve.
$AUC_{\text{last}}^a$	Area under the concentration-time profile from time zero to the time of the last quantifiable concentration ( $C_{\text{last}}$ )	Linear/log trapezoidal method
$AUC_{\text{inf}}^a$	Area under the concentration-time profile from time zero extrapolated to infinite time	$AUC_{\text{last}} + (C_{\text{last}}^*/k_{el})$ , where $C_{\text{last}}^*$ is the predicted plasma concentration at the last quantifiable time point estimated from the log-linear regression analysis.
$CL^{a,b}$	Systemic clearance	Dose/ $AUC_{\text{inf}}$
$V_{ss}^{a,b}$	Steady-state volume of distribution following IV infusion	$V_{ss} = CL \times [MRT - (\text{infusion time}/2)]$ where MRT is the Mean Residence Time and is calculated as $AUMC_{\text{inf}}/AUC_{\text{inf}}$

a. If data permit

b. PF-07304814 only

PK samples will be stored and may be used in the future for CCI  
 CCI scientific purpose, as needed.

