6.3.2. PK Parameter Endpoints

- **Plasma PK Parameters**

Plasma PF-07304814 and PF-00835231 (active moiety) concentrations will be reported in units of mass per volume, while total [^{14}C] in plasma will be reported in units of unchanged drug concentration equivalents per volume (eg, ngEq/mL). PK parameters (Table 1) will be derived from PF-07304814 and PF-00835231 concentrations in plasma and from total [^{14}C] concentration equivalents in plasma. Actual PK sampling times will be used for the derivation of PK parameters.

The PF-07304814 and PF-00835231 concentrations and PK parameters and the total [^{14}C] concentration equivalents and PK parameters will be listed and summarized using descriptive statistics. Individual and median PF-07304814 and PF-00835231 concentration-time profiles and total [^{14}C] concentration equivalents-time profiles will be graphically presented.

Table 1. Noncompartmental PK Parameters of Plasma

Parameter	Analysis Scale	PF-07304814	PF-00835231	total [^{14}C]
AUC _{inf} ^a	ln	D	D	D
AUC _{last} ^a	ln	D	D	D
C _{max}	ln	D	D	D
T _{max}	R	D	D	D
C ₂₄	R	D	D	D
t _{1/2} ^a	R	D	D	D
CL ^{a,b}	ln	D		
V _{ss} ^{a,b}	ln	D		

Key: a=if data permits, b=PF-07304814 only, D=displayed with descriptive statistics, ln=natural-log transformed, R=raw (untransformed)

- **Urine PK Parameters**

Total urine [^{14}C] concentrations and percent [^{14}C] will be listed and summarized using descriptive statistics. Individual and summary profiles of urine [^{14}C] will be graphically presented.

Data permitting, following urine parameters will be calculated:

Table 2. Noncompartmental PK Parameters of Urine

Parameter	Analysis Scale	PF-07304814	Total [^{14}C]
Total [^{14}C] Urine	R	D	D
% [^{14}C] Urine	R	D	D

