7.1. Concentrations Below the Limit of Quantification

In all data presentations (except listings), concentrations below the limit of quantification (BLQ) will be set to zero. (In listings BLQ values will be reported as “<LLQ”, where LLQ will be replaced with the value for the lower limit of quantification).

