7.3. Pharmacokinetic Parameters

Actual PK sampling times will be used in the derivation of PK parameters.

If a PK parameter cannot be derived from a participant's concentration data, the parameter will be coded as NC (ie, not calculated). (Note that NC values will not be generated beyond the day that a participant discontinues).

In summary tables, statistics will be calculated by setting NC values to missing; and statistics will be presented for a particular renal function group with ≥ 3 evaluable measurements.

If an individual participant has a known biased estimate of a PK parameter (due for example to an unexpected event such as vomiting before all the compound is adequately absorbed in the body), this will be footnoted in summary tables and will not be included in the calculation of summary statistics or statistical analyses.

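### If PF-07304814 again falls below the assay limit after 16 h, its AUClast will end at 12 h because nothing is sampled between 12 h and 24 h; separately, its CL and Vss will not be calculable

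*Protocol*

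**What the plan says.** **Earlier data.** Protocol Section 2.2.4.2 describes single 24-hour infusions of 50, 150, 500 and 700 mg in healthy participants. Prodrug levels were close to their maximum from about 3 h until at least 16 h. Then: "Despite a continuous 24-hour infusion of PF-07304814, plasma concentrations declined before the end of the infusion". No half-life was obtained because "all plasma samples collected after the 16 hours post start of the infusion were below the limit of detection". The section gives 40 ng/mL as the lower limit of detection. Neither document states the limit of the assay for this study; protocol Section 8.4.1 says only that the method is validated.

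**Sampling.** Schedule of Activities, footnote o, sets the blood draws for unlabeled drug before dosing "and at 0.5, 1, 2, 6, 12, 24 (to be taken immediately prior to end of infusion), 25, 27, 32, 48" and on to 216 h.

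**Parameters.** Protocol Section 3 lists AUClast, AUCinf, Cmax, Tmax, C24, CL, Vss and t1/2 as primary plasma endpoints, without caveat. Protocol Table 1 marks AUClast, AUCinf, t1/2, CL and Vss as dependent on the data, and restricts CL and Vss with the footnote "b. PF-07304814 only". The key to SAP Table 1 repeats both conditions: "a=if data permits, b=PF-07304814 only". SAP Section 7.3 provides that a parameter which cannot be derived is coded NC and treated as missing in summaries. Neither document names a fixed-interval AUC or a clearance based on Css, although Css was reported for the prodrug in the earlier study.

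**The concern.** The earlier study used the same infusion length and included the same dose. If its prodrug profile recurs, the sample just before the end of infusion and every sample after it would be below the limit. The last usable prodrug concentration would be at 12 h, although the earlier data suggest that measurable levels last to at least 16 h. Prodrug exposure, part of a primary objective, would then rest on the first half of the infusion. With about 5 participants and a single dose, a missed time point cannot be recovered, and an exposure measure chosen after the values are seen would be post hoc.

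The same pattern would leave no terminal phase. That is a second problem with a different cause.

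**Working it through.** The plan gives no figure of its own to reproduce. The check sets the sampling times against the earlier 16 h cut-off, follows the Table 1 formulas, and sizes the truncation.

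**1. Samples lost on recurrence.** There are 15 draws after the start of infusion: 0.5, 1, 2, 6 and 12 h, then 24, 25, 27, 32, 48, 72, 96, 120, 144 and 216 h. None lies between 12 h and 24 h. Ten of the 15 are at or after 24 h and would be below the limit. The last quantifiable time is 12 h.

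**2. Problem (a): AUClast.** Table 1 ends AUClast at the last quantifiable concentration, so it becomes AUC0-12. To size this, assume a profile with a plateau of 1 unit that is flat to 16 h, and compare the area to 12 h with the area to 16 h. The loss is (A16 - A12)/A16.

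| Assumed rise to plateau | A12 | A16 | Loss |
|---|---|---|---|
| Immediate (exact area) | 12 | 16 | 25.0% |
| Exponential, 95% at 3 h (planned grid) | 10.82 | 14.82 | 27.0% |
| Exponential, 90% at 3 h (planned grid) | 10.47 | 14.47 | 27.6% |
| Linear to 3 h (exact area) | 10.5 | 14.5 | 27.6% |
| Linear to 3 h (planned grid) | 10.0 | 14.0 | 28.6% |
| Exponential, 80% at 3 h (planned grid) | 9.87 | 13.87 | 28.8% |

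For the linear rise on the planned grid, the concentrations at 0, 0.5, 1, 2, 6 and 12 h are 0, 1/6, 1/3, 2/3, 1 and 1. The trapezoids are 0.042 + 0.125 + 0.5 + 3.333 + 6 = 10.0, and a 16 h sample adds 4.0.

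Measured against the true area to 24 h for the linear rise, the result depends on the unknown decline. If levels vanish just after 16 h (true area 14.5), AUClast to 12 h captures 10.0/14.5 = 69%, and a 16 h sample raises that to 14.0/14.5 = 97%. If levels fall linearly to zero at 24 h (true area 14.5 + 4.0 = 18.5), the figures are 54% and 76%.

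**3. Problem (b): CL and Vss.** From Table 1:

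- kel is the log-linear slope of the terminal phase;
- AUCinf = AUClast + Clast*/kel;
- CL = Dose/AUCinf;
- Vss = CL x (MRT - infusion time/2), with MRT = AUMCinf/AUCinf.

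Without a post-infusion concentration there is no kel, so t1/2, AUCinf, CL and Vss all become NC. A 16 h sample does not change this: on a flat plateau the log slope over 6, 12 and 16 h is 0. The documents set no acceptance rule for kel, so this step assumes the usual practice of not fitting a terminal slope to samples taken during the infusion.

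**4. How far the assay could change this.** Suppose, as an assumption, that C24 is at most 40 ng/mL. The level at time t is then at most 40 x 2^(-(t - 24)/h) for half-life h. With h = 1.97 h, which is the active moiety's mean at 500 mg and is borrowed here, the level at 27 h is 13.9 ng/mL. A kel from 24, 25 and 27 h would then need an assay at least about 2.9-fold more sensitive. Over assumed half-lives of 4 h down to 1 h the requirement runs from 1.7-fold to 8-fold. Protocol Section 2.2.2 calls prodrug metabolism rapid, so 1 h is not a lower bound. The range is too wide to say whether a better assay would rescue kel.

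**The case against.** The strongest case against acting has four parts.

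- **The plan already allows for this.** Table 1 makes the affected parameters conditional on the data, and SAP Section 7.3 says what happens otherwise: "the parameter will be coded as NC (ie, not calculated"). That stands. The loss of CL and Vss is foreseen, and in a descriptive study a blank parameter is a legitimate outcome.
- **Measures that need no kel remain.** AUClast, Cmax and Tmax can still be derived, and the earlier study judged dose proportionality from AUClast and Cmax. AUC0-12 could even be pre-specified with no new sample. No objective here requires comparison with the earlier study. This largely stands and limits the severity. It does not answer why prodrug exposure should stop at 12 h when one draw would extend it.
- **The premise may not hold.** The assay limit is not given and the earlier decline is not explained. This stands, so the point is conditional. Even with a better assay, one trapezoid would span the 12 hours in which the decline occurred.
- **The schedule is already flexible.** Protocol Section 8.4.1 lets times move and lets time points be added without an amendment. This stands, and it is what makes the fix cheap.

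A reader might infer that the 12 h to 24 h gap is what costs the study CL and Vss. The documents do not support that: the earlier study described levels to at least 16 h and still had no half-life. A reader might also infer that a below-limit C24 shown as zero would mislead. SAP Section 8.2.1 puts the count of values above the limit beside the summary, and SAP Section 7.1 keeps the limit itself visible in listings.

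**Conclusion.** The point holds as a minor, conditional improvement with two distinct parts. If the earlier pattern recurs at a similar assay limit:

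- the sampling gap ends prodrug AUClast at 12 h, about 25% to 29% below AUC to 16 h, assuming levels near plateau by about 3 h and flat to 16 h;
- the absence of a measurable terminal phase, and not the gap, leaves prodrug t1/2, AUCinf, CL and Vss as NC. Since CL and Vss are planned for the prodrug only, the study would report neither.

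It would go too far to say that the primary PK objective fails. Prodrug Cmax and Tmax remain estimable, and PF-00835231 parameters, total [14C] parameters and mass balance are not affected. What is missing is a sample inside the window where levels are expected to be measurable, and a named exposure measure for the case where kel cannot be estimated.

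**What to change.** 1. **Sample at 16 h for unlabeled PF-07304814 and PF-00835231 only.** Either add it to the Schedule of Activities and footnote o, or move one late unlabeled sample so that the number stays the same. Moving one should cost little for the active moiety: at a half-life of 1.97 h about 0.02% of the end-of-infusion level is left by 48 h (2^(-24/1.97) = 0.0002). Section 8.4.1 also names PF-07319509 and PF-03626560 for these samples, so check them before a late sample is given up. No extra [14C] draw is needed.

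2. **Pre-specify a fixed-interval prodrug AUC,** for example AUC0-16, in protocol Table 1 and SAP Section 6.3.2, as the exposure measure when kel is not estimable. State how a below-limit value at 16 h is handled.

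3. **Optionally, report a supportive CL as infusion rate/Css.** The rate is 500 mg/24 h = 20.8 mg/h, with Css taken over a named window such as the 6, 12 and 16 h samples. State its steady-state assumption as a limitation, because the decline during infusion is unexplained.

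These changes do not restore kel, AUCinf or the planned CL and Vss, and no substitute for Vss is offered.

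**Cost.** An added sample takes about 4 mL per participant (about 280 to 284 mL, against the 500 mL ceiling in protocol Section 8) and one more assay; a moved sample adds neither. With a start at 08:00 plus or minus 2 hours, the draw falls between 22:00 and 02:00, when participants are already confined. If a sample is added, reconcile the sentence in Section 8.4.1 that fixes the number of samples with the one that allows additions. The parameter change is a few lines, with a protocol amendment only if the sponsor judges it a major change to a primary endpoint definition under protocol Section 9.

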### **2.3. Benefit/Risk Assessment**

PF-07304814 will not provide any clinical benefit to healthy participants. This study is designed primarily to further the understanding of human PK, metabolism, and elimination of PF-07304814 and PF-00835231 (active moiety).

Since the administered radioactivity is very low (eg, <1000 nCi), participants will be exposed to extremely low amounts of radiation and therefore supporting data such as a dosimetry study in animals are not required.

More detailed information about the known and expected benefits and risks and reasonably expected adverse events of PF-07304814 may be found in the investigator's brochure, which is the SRSD for this study.

### 2.3.1. Risk Assessment

Potential Risk of Clinical Significance	Summary of Data/Rationale for Risk	Mitigation Strategy
Study Intervention(s) PF-07304814		
Potential risks associated with PF-07304814 include inflammatory effects, noted by changes in peripheral blood WBCs, coagulation parameters, inflammatory cell infiltrates in various tissues, and thromboemboli at the infusion site and/or in different tissues.	
The potential risks are based on the nonclinical study findings. Thrombosis and increased inflammation were observed following prolonged exposure of PF-07304814 noted in the 14-day NHP toxicology study.
 
Information is available in the SRSD for PF-07304814.
	
As this is an investigational agent, there is some risk that is mitigated by close observation of AEs, vital signs, ECGs and laboratory assessments.
 
Participants with a history of thrombotic events will be excluded.

Study Procedures		
Potential for irritation at the intravenous catheterization site which is required for administration of the study intervention.	Intravenous catheterization may cause pain at the site of insertion, bruising, hematoma formation, bleeding, extravasation, and possibly infection at the catheter site, or bloodstream infection.	Aseptic technique may mitigate the risk of infection. Other adverse effects can be managed via local care (eg, applying pressure to the site to stop bleeding) and/or analgesia.
Potential for increased risk of intravenous infusion site reaction.	There may be potential risk for infusion site reaction due to the low pH of study intervention and/or the need for continuous intravenous infusion. These risks are described in the SRSD for PF-07304814.	
Monitoring of reactions will be performed through targeted PE and collection of AEs, which will be reviewed on an ongoing basis.
 
If an individual participant is unable to tolerate the continuous infusion, based on AEs, treatment may need to be discontinued.

Other (Not Applicable)		

PFIZER CONFIDENTIAL

